8.3 Dose modifications for pomalidomide based on adverse events during a cycle

(For each cycle during induction and consolidation and maintenance)

Table 8.3			
CTCAE System/Organ/Class (SOC)	ADVERSE EVENT	AGENT	ACTION**
Investigations	Neutrophil count decreased If ANC $<1.0 \times 10^9/L$ or ANC $>1.0 \times 10^9/L$ (up to LLN) with fever (temperature $>38.5^\circ C$)	Pomalidomide	Omit pomalidomide dose. Follow CBC weekly. If neutropenia has resolved to \leq Grade 2 prior to Day 21 and fever has resolved, restart pomalidomide at next lower dose level and continue through Day 21 of a 28-day cycle. If febrile neutropenia is the only toxicity for which a dose reduction is required, G-CSF may be used and the pomalidomide dose maintained.
Investigations	Platelet count decreased If platelet count $<30 \times 10^9/L$	Pomalidomide	Omit pomalidomide dose Follow CBC weekly Hold anticoagulation/antiplatelet therapy until platelets $\geq 50,000/mm^3$ If platelet count resolves to \leq Grade 2 prior to Day 21, restart pomalidomide at next lower dose level and continue through Day 21 of each cycle
Skin and subcutaneous tissue disorders	Rash maculopapular Grade 2 or 3	Pomalidomide	Omit pomalidomide dose; follow weekly If the AE resolves to \leq Grade 1 prior to Day 21, restart pomalidomide at next lower dose level and continue through Day 21 of each cycle
	Grade 3-4 Stevens –Johnson Syndrome	Pomalidomide	Discontinue pomalidomide and remove patient from all study treatment
	\geq Grade 3 Erythema multiforme	Pomalidomide	Discontinue pomalidomide and remove patient from all study treatment

Table 8.3			
CTCAE System/Organ/Class (SOC)	ADVERSE EVENT	AGENT	ACTION**
	Erythroderma ≤Grade 3	Pomalidomide	Omit pomalidomide dose; follow weekly If the AE resolves to ≤Grade 1 prior to Day 21, restart pomalidomide at next lower dose level and continue through Day 21 of the 28-day cycle
	Rash, maculo-papular Rash, acneiform Grade 4	Pomalidomide	Discontinue pomalidomide and remove patient from all study treatment
Nervous system disorders	Peripheral sensory neuropathy Grade 3	Pomalidomide	Omit pomalidomide dose and follow at least weekly. If the AE resolves to ≤Grade 1 prior to Day 21, restart pomalidomide at next lower dose level and continue through Day 21 of the 28-day cycle
	Peripheral sensory neuropathy Grade 4	Pomalidomide	Discontinue pomalidomide and remove patient from all study treatment
Immune system disorders	Allergic reaction Grade 2-3	Pomalidomide	Omit dose and follow at least weekly If the AE resolves to ≤Grade 1 prior to Day 15, restart at next lower dose level and continue through Day 21 of the 28-day cycle
	Allergic reaction Grade 4	Pomalidomide	Discontinue pomalidomide and remove patient from all study treatment
Vascular disorders	Thromboembolic event ≥ Grade 3	Pomalidomide	Omit dose and start anticoagulation Restart at investigator's discretion (maintain dose level)
Endocrine disorders	Hyperthyroidism or Hypothyroidism ≥ Grade 2	Pomalidomide	Omit pomalidomide for remainder of cycle, evaluate etiology, and initiate appropriate therapy See Instructions for Initiation of a New Cycle and reduce the dose of pomalidomide by 1 dose level.

Table 8.3			
CTCAE System/Organ/Class (SOC)	ADVERSE EVENT	AGENT	ACTION**
Other non-hematologic adverse event	Other non-hematologic \geq Grade 3	Pomalidomide	If the AE can be attributed to either of the drugs, pomalidomide should be discontinued at first instance followed by ixazomib for recurrence of the same toxicity necessitating dose modification Omit pomalidomide dose. Follow at least weekly If the toxicity resolves to \leq Grade 2 prior to Day 21, restart pomalidomide at next lower dose level and continue through Day 21 of the 28-day cycle

* Located at http://ctep.cancer.gov/protocolDevelopment/electronic_applications.ctc.htm

** Use the following to describe actions in the Action column:

- Omit = The current dose(s) for the specified drug(s) during a cycle is skipped. The patient does not make up the omitted dose(s) at a later time
- Hold/Delay = The current dose(s) of all drugs during a cycle is delayed. The patient does make up the delayed dose(s) when the patient meets the protocol criteria to restart drugs.
- Discontinue = The specified drug(s) are totally stopped.

NOTE: For adverse events attributable to both ixazomib and pomalidomide, only one of the drugs should be reduced for each incidence of toxicity severe enough to necessitate dose reduction. The drug reduced should alternate starting with pomalidomide for the first dose reduction.

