	Grade 2 with pain or Grade 3	Ixazomib	Omit ixazomib until AE resolves or returns to baseline. When AE resolves, re-initiate ixazomib at the next lower dose level.
	Grade 4	Ixazomib	Omit ixazomib. Peripheral neuropathy should be monitored until toxicity resolves or returns to baseline. Upon recovery, if the patient has received clinical benefit from therapy with ixazomib, the investigator may consider restarting ixazomib at the next lower dose level
Skin and subcutaneous tissue disorders	Rash, maculo-papular Rash, acneiform Grade 2 or 3	Ixazomib	Omit ixazomib until rash resolves to \leq Grade 1 (See Section 9.9a). Restart at same dose. If the rash recurs, reduce dose by one dose level.
	Grade 4		Discontinue ixazomib

CTCAE System/Organ/Class (SOC)	ADVERSE EVENT	AGENT[#]	ACTION^{**}
Other	Any other non-hematological Grade 3 attributable adverse event except:	Ixazomib Pomalidomide Dexamethasone	Omit ixazomib or pomalidomide or both depending on the attribution to either or both drugs, until resolution to Grade ≤1 or baseline. Restart at next lower dose - If a patient is already at the lowest drug level, go to event monitoring. If the toxicity can be attributed to either of the drugs, pomalidomide should be discontinued at first instance followed by ixazomib for recurrence of the same toxicity necessitating dose modification.
Gastrointestinal Disorders	Grade 3 nausea and/or emesis in the absence of optimal anti-emetic prophylaxis Grade 3 diarrhea that occurs in the absence of optimal supportive therapy		
General disorders and administration site conditions	Grade 3 fatigue (consider relatedness to one or all of the components of the combination)		
Other	Grade 4 Nonhematologic adverse events (consider relatedness to one or all of the components of the combination)	Ixazomib Pomalidomide Dexamethasone	Consider permanently discontinuing ixazomib or pomalidomide or dexamethasone or all three depending on the attribution to either one, two or all three drugs (exception would be if the investigator determines the patient is obtaining a clinical benefit) If both ixazomib and pomalidomide are discontinued, the patient will go to event monitoring.

* Located at http://ctep.cancer.gov/protocolDevelopment/electronic_applications.ctc.htm

** Use the following to describe actions in the Action column:

- Omit = The current dose(s) for the specified drug(s) during a cycle is skipped. The patient does not make up the omitted dose(s) at a later time

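### The catch-all rows of Tables 8.2 and 8.3 set different pomalidomide restart rules for the same unnamed non-hematologic event, and nothing says which governs

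*Combined protocol and SAP*

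**What the plan says.** Section 8 holds two sets of catch-all instructions for non-hematologic events that reach pomalidomide.

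- **Table 8.2, 'Other', Grade 3.** The table is titled for ixazomib, but this row also lists pomalidomide and dexamethasone as agents. The action is: "Omit ixazomib or pomalidomide or both depending on the attribution to either or both drugs, until resolution to Grade ≤1 or baseline", then restart one level lower. Three kinds of Grade 3 event are carved out: nausea or vomiting without optimal antiemetics, diarrhea without optimal supportive therapy, and fatigue.
- **Table 8.2, 'Other', Grade 4.** The same three agents are listed. The action is: "Consider permanently discontinuing ixazomib or pomalidomide or dexamethasone or all three depending on the attribution to either one, two or all three drugs". It is qualified by: "exception would be if the investigator determines the patient is obtaining a clinical benefit". The row gives no restart grade.
- **Table 8.3, 'Other non-hematologic', Grade 3 or higher.** Pomalidomide is omitted and followed at least weekly; the drug comes back once the toxicity is at or below "Grade 2 prior to Day 21, restart pomalidomide at next lower dose level and continue through Day 21 of the 28-day cycle". The row opens with an attribution clause: "If the AE can be attributed to either of the drugs, pomalidomide should be discontinued at first instance followed by ixazomib".

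Table 8.3 also has one erythroderma row, printed as "Erythroderma ≤Grade 3", which requires Grade 1 or less before a same-cycle restart. No other erythroderma rule appears in the documents.

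**The concern.** A single event can satisfy a row in each table, and the two rows then lead to different actions. An investigator who opens the pomalidomide table for a pomalidomide reaction finds the looser limit. One who opens Table 8.2, despite its ixazomib title, finds the stricter one. Section 8.0 asks for strict adherence in the first two cycles, so the plan is firmest in the period when these two rows cannot both be followed.

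What is at stake is patient safety and uniform handling. A patient with a recent Grade 3 or 4 reaction that is still at Grade 2 may be re-exposed in mid-cycle under one row and kept off the drug under the other.

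**Working it through.** No arithmetic is involved beyond a count. The check sets the rules side by side for a non-hematologic event that is attributed to pomalidomide alone and not named in Table 8.3.

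| Event grade | Table 8.2 | Table 8.3 'Other' | Compatible? |
|---|---|---|---|
| 3 | Omit until Grade 1 or less, or baseline; restart one level lower | Omit; restart one level lower at Grade 2 or less before Day 21 | No, if the event sits at Grade 2 and baseline was lower |
| 4 | Consider permanent stop; clinical-benefit exception; no restart grade | Same as for Grade 3 | Only if read in sequence, which is not stated |

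**Step 1: which limit is the outlier?** Seven recovery limits in Section 8 name a grade for non-hematologic events and apply to pomalidomide:

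- Table 8.3: maculopapular rash, erythroderma, sensory neuropathy and allergic reaction, all at Grade 1 or less (4).
- Table 8.2: other Grade 3 events, at Grade 1 or less, or baseline (1).
- Section 8.11: start of a new cycle, at Grade 1 or less, or baseline (1).
- Table 8.3: 'Other', at Grade 2 or less (1).

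So 4 + 1 + 1 = 6 of 7 sit at Grade 1 (or baseline) and one sits at Grade 2. Without Section 8.11, which governs new cycles rather than same-cycle restarts, the count is 5 of 6. The thromboembolic and thyroid rows and the Grade 4 row of Table 8.2 name no recovery grade and are not counted. The neutrophil and platelet rows of Table 8.3 do use Grade 2, but for blood counts.

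**Step 2: does any text rank the rows?**

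- The greatest-reduction sentence in Section 8.0 concerns several adverse events at once, not one event that meets two rows.
- The note under Tables 8.2 and 8.3 on alternating reductions concerns events attributable to both drugs.
- The attribution clause in the 'Other' row concerns events that either drug could have caused.
- Section 8.11 controls the start of a new cycle, not a restart within one.

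None of these settles the question.

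**Step 3: an illustrative case.** A patient on 4 mg in induction has an unnamed Grade 3 event from a baseline of Grade 0, and it has eased to Grade 2 by Day 15. Under Table 8.3, pomalidomide restarts at 3 mg and runs to Day 21. Under Table 8.2, it stays off. If the event is still Grade 2 on Day 1 of the next cycle, Section 8.11 holds the whole cycle. The drug would have been given in mid-cycle at a severity that bars it at the start of the next.

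**Step 4: where erythroderma fits.**

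- *If the sign is correct (Grade 3 or lower):* Grade 4 has no row of its own and falls to the catch-all rows. The 'Other' row would then apply a looser limit (Grade 2) than milder erythroderma receives (Grade 1). But the row would also trigger at Grade 1, where its restart condition is met at onset. No other Table 8.3 row with a stated recovery grade behaves that way.
- *If the sign should be Grade 3 or higher:* Grade 4 is covered by the row, with restart at Grade 1 or less, and there is no inversion.

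The documents cannot settle the sign. The Grade 3 and Grade 4 catch-all problems above stand either way.

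**The case against.** The best reply is that the two Grade 4 rows answer different questions. Table 8.2 asks whether to stop for good; Table 8.3 says how to restart if the drug is not stopped. In that order both can be followed. This is a fair reading, and it reduces the Grade 4 problem to an unstated order and a loose limit. It does not help at Grade 3, where both rows set a numeric limit for the same restart and the limits differ.

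The reach is also limited, and this stands. After two cycles the tables are only guidelines. The gap matters only when an event attributed to pomalidomide alone sits at Grade 2, above baseline, before Day 21. No row compels rechallenge, because Section 13.4 lets the investigator stop treatment. Section 16.42 counts related Grade 4 or higher non-hematologic events, Section 10.4 requires expedited reporting of serious events, and Section 9.9a recommends a dermatology consult for Grade 3 or higher rash. None of these sets a restart grade.

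A reader might infer something stronger: that the protocol plainly omits a Grade 4 erythroderma rule and ought to mandate removal from all treatment, as it does for the other named skin events. The documents do not support that. The inference depends on a doubtful sign, and Table 8.2 does address Grade 4. Stevens-Johnson syndrome and erythema multiforme already stop pomalidomide from Grade 3, so they are weak evidence of an intended Grade 4 rule for erythroderma. Stopping at Grade 4 is not universal in Table 8.3 either: thromboembolic events of Grade 3 or higher may restart at the same dose.

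**Conclusion.** The point holds as a minor conflict between stated rules. At Grade 3 it is direct: Grade 1 or baseline in one table, Grade 2 in the other. At Grade 4 it is an unranked overlap, in which the only numeric same-cycle limit is the looser one. Erythroderma is an example only if the printed sign is right.

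The conclusion assumes attribution to pomalidomide alone, a baseline below Grade 2 and, for the Grade 3 conflict, an event outside the Table 8.2 carve-outs. With 25 planned patients and rare events, few if any patients would be affected. The primary endpoint, the 0.095 significance level and the power are untouched.

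**What to change.** 1. In the 'Other non-hematologic' row of Table 8.3, change the restart limit from Grade 2 or less to Grade 1 or less, or baseline. This matches Table 8.2 and Section 8.11.
2. Add to Section 8.3: *For Grade 4 non-hematologic events not named in Table 8.3, first apply the Grade 4 row of Table 8.2; if pomalidomide is not permanently discontinued, restart one dose level lower only after resolution to Grade 1 or less, or baseline.*
3. Check the erythroderma sign against the source and correct it if needed. Whether Grade 4 erythroderma should mean removal from all study treatment is for the clinical team to decide; it would also take the patient off ixazomib.

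The cost is one row edit, one sentence and one check. Some patients will restart slightly later within a cycle, and investigators lose a little discretion. The new limit would also apply to the Grade 3 events that Table 8.2 carves out (such as fatigue) when they are attributed to pomalidomide; if the team wants Grade 2 kept for those, the row should say so. Nothing in the analysis or sample size changes.

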8.4 Dose modifications for dexamethasone based on adverse events during a cycle

(for each cycle during induction and consolidation and maintenance)

Table 8.4			
CTCAE System/Organ/Class (SOC)	ADVERSE EVENT	AGENT	ACTION**
Gastrointestinal disorders	Dyspepsia Grade 1-2	Dexamethasone	Treat with H2 blockers, sucralfate, or omeprazole If symptoms persist despite above measures, decrease dexamethasone dose by 1 dose level
	Gastric or duodenal ulcer Grade 1-2	Dexamethasone	Treat with H2 blockers, sucralfate, or omeprazole If symptoms persist despite above measures, decrease dexamethasone dose by 1 dose level
	Gastritis Grade 1-2	Dexamethasone	Treat with H2 blockers, sucralfate, or omeprazole If symptoms persist despite above measures, decrease dexamethasone dose by 1 dose level
	Dyspepsia ≥Grade 3	Dexamethasone	Omit dexamethasone until symptoms adequately controlled Restart one dose level below along with concurrent therapy with H2 blockers, sucralfate, or omeprazole If symptoms persist despite above measures, discontinue dexamethasone and do not resume Ixazomib and pomalidomide should be continued
	Gastric or duodenal ulcer ≥Grade 3	Dexamethasone	Omit dexamethasone until symptoms adequately controlled Restart one dose level below along with concurrent therapy with H2 blockers, sucralfate, or omeprazole If symptoms persist despite above measures, discontinue dexamethasone and do not resume Ixazomib and pomalidomide should be continued

Table 8.4			
CTCAE System/Organ/Class (SOC)	ADVERSE EVENT	AGENT	ACTION**
	Gastritis \geq Grade 3	Dexamethasone	Omit dexamethasone until symptoms adequately controlled Restart one dose level below along with concurrent therapy with H2 blockers, sucralfate, or omeprazole If symptoms persist despite above measures, discontinue dexamethasone and do not resume Ixazomib and pomalidomide should be continued
	Pancreatitis \geq Grade 3 (Severe pain; vomiting; medical intervention indicated (e.g., analgesia, nutritional support))	Dexamethasone	Discontinue dexamethasone and do not resume Ixazomib and pomalidomide should be continued
General disorders and administration site conditions	Edema (any location) \geq Grade 3 (limiting function and unresponsive to therapy or anasarca)	Dexamethasone	Diuretics as needed, and decrease dexamethasone dose by 1 dose level If edema persists despite above measures, decrease dose another dose level Discontinue dexamethasone and do not resume if symptoms persist despite second reduction Ixazomib and pomalidomide should be continued
Psychiatric disorders	Delirium, delusion, depression, hallucination, euphoria \geq Grade 2	Dexamethasone	Omit dexamethasone until symptoms resolve Restart with one dose level reduction If symptoms persist despite above measures, discontinue dexamethasone and do not resume Ixazomib and pomalidomide should be continued

Table 8.4			
CTCAE System/Organ/Class (SOC)	ADVERSE EVENT	AGENT	ACTION**
Musculoskeletal and connective tissue disorders	Muscle weakness (any location) ≥ Grade 2 Weakness limiting self-care ADL; disabling	Dexamethasone	Decrease dexamethasone dose by one dose level; if weakness persists despite above measures decrease dose by one additional dose level Discontinue dexamethasone and do not resume if symptoms continue to persist Ixazomib and pomalidomide should be continued
Metabolism and nutrition disorders	Hyperglycemia ≥ Grade 3 (>250 - 500 mg/dL; >13.9 - 27.8 mmol/L); hospitalization indicated	Dexamethasone	Treatment with insulin or oral hypoglycemics as needed If uncontrolled despite above measures, decrease dose by one dose level at a time until levels are satisfactory

* Located at http://ctep.cancer.gov/protocolDevelopment/electronic_applications.ctc.htm

** Use the following to describe actions in the Action column:

- Omit = The current dose(s) for the specified drug(s) during a cycle is skipped. The patient does not make up the omitted dose(s) at a later time
- Hold/Delay = The current dose(s) of all drugs during a cycle is delayed. The patient does make up the delayed dose(s) when the patient meets the protocol criteria to restart drugs.
- Discontinue = The specified drug(s) are totally stopped.

9.0 Ancillary Treatment/Supportive Care

9.1 Full supportive care

Patients should receive full supportive care while on this study. This includes blood product support, antibiotic treatment, and treatment of other newly diagnosed or concurrent medical conditions. All blood products and concomitant medications such as antidiarrheals, analgesics, and/or antiemetics received from the first day of study treatment administration until 30 days after the final dose will be recorded in the medical records.

9.2 Steroid use

Patients may continue on low level/stable steroid doses for replacement or inhalation therapy.

9.3 Disallowed concurrent treatment

The following treatments are not permitted during the trial:

- Any other investigational treatment
- Any other systemic anti-neoplastic therapy including, but not limited to, immunotherapy, hormonal therapy or monoclonal antibody therapy.
- Any external beam radiotherapy

9.4 Nausea and/or vomiting:

Standard anti-emetics including 5-hydroxytryptamine 3 serotonin receptor antagonists are recommended for emesis if it occurs once treatment is initiated; prophylactic anti-emetics may also be considered at the physician's discretion. Dexamethasone should not be administered as an anti-emetic. Fluid deficit should be corrected before initiation of study drug and during treatment.

9.5 Blood products and growth factors

Blood products and growth factors should be utilized as clinically warranted and following institutional policies and recommendations. The use of growth factors should follow published guidelines of the Journal of Clinical Oncology, Vol 24, No 18 (June 20), 2006: pp. 2932-2947.

NOTE: Platelet transfusions to help patients meet eligibility criteria are not allowed within 3 days prior to study registration or drug dosing for any dosing day.

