3.0 Patient Eligibility

3.1 Inclusion Criteria

- 3.11 Age ≥ 18 years.
- 3.12 Previously treated ASCT naïve MM patients, currently with relapsed or refractory disease who are being considered for single ASCT for relapsed disease. Patients must be eligible to undergo a stem cell transplant as per institutional criteria for selection at the time of registration.
- 3.13 The following laboratory values obtained ≤ 14 days prior to registration.
- Calculated creatinine clearance (using Cockcroft-Gault equation below)* ≥ 30 mL/min
 - Absolute neutrophil count (ANC) $\geq 1000/\text{mm}^3$
 - Platelet count $\geq 75 \times 10^9/\text{L}$ unless the participant has $\geq 50\%$ bone marrow infiltration in which case a platelet count of $\geq 50 \times 10^9/\text{L}$ is allowed
 - Hemoglobin ≥ 9.0 g/dL
 - Total bilirubin $\leq 1.5 \times$ the upper limit of the normal range (ULN) or if total bilirubin is $> 1.5 \times$ ULN, the direct bilirubin must be ≤ 2.0 mg/dL.
 - Alanine aminotransferase (ALT) and aspartate aminotransferase (AST) $\leq 3 \times$ ULN or $< 5 \times$ ULN if liver involvement

*Cockcroft-Gault Equation:

$$\text{Creatinine clearance for males} = \frac{(140 - \text{age})(\text{actual body weight in kg})}{(72)(\text{serum creatinine in mg/dL})}$$

$$\text{Creatinine clearance for females} = \frac{(140 - \text{age})(\text{actual body weight in kg})(0.85)}{(72)(\text{serum creatinine in mg/dL})}$$

- 3.14 Patients with measurable disease defined as at least one of the following:
- Serum monoclonal protein ≥ 1.0 g/dL by protein electrophoresis
 - ≥ 200 mg of monoclonal protein in the urine on 24-hour electrophoresis
 - Serum immunoglobulin free light chain ≥ 10 mg/dL AND abnormal serum immunoglobulin kappa to lambda free light chain ratio.
- 3.15 ECOG performance status (PS) 0, 1 or 2 ([Appendix I](#)).
- 3.16 Willing to provide informed written consent.
- 3.17 Negative pregnancy test done ≤ 7 days prior to registration, for persons of childbearing potential only.
- 3.18 Willing to follow strict birth control measures.
- Persons of childbearing potential, agree to one of the following:
- Practice 2 effective methods of contraception, at the same time, from the time of signing the informed consent form through 90 days after the last dose of study drug, AND must also adhere to the guidelines of any treatment-specific pregnancy prevention program, if applicable, OR

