3.2 Exclusion Criteria

- 3.21 Diagnosed or treated for another malignancy ≤ 2 years prior to registration or previously diagnosed with another malignancy and have any evidence of residual disease.
NOTE: If there is a history or prior malignancy, patient must not be receiving other specific treatment for their cancer. Patients with non-melanoma skin cancer or carcinoma in situ of any type, or low-risk prostate cancer after curative therapy, are not excluded if they have undergone complete resection.
NOTE: Platelet transfusions to help patients meet eligibility criteria are not allowed ≤ 3 days prior to study registration.
- 3.22 Any of the following because this study involves an investigational agent whose genotoxic, mutagenic and teratogenic effects on the developing fetus and newborn are unknown:
 - Pregnant persons
 - Nursing persons
 - Persons of childbearing potential who are unwilling to employ adequate contraception
- 3.23 Co-morbid systemic illnesses or other severe concurrent disease which, in the judgment of the investigator, would make the patient inappropriate for entry into this study or interfere significantly with the proper assessment of safety and toxicity of the prescribed regimens. **NOTE:** this includes uncompensated heart or lung disease.
- 3.24 Receiving any other investigational agent which would be considered as a treatment for the primary neoplasm. **NOTE:** Bisphosphonates are considered to be supportive care rather than therapy and are allowed while on protocol treatment.
- 3.25 Patient has \geq Grade 2 peripheral neuropathy, or Grade 1 with pain on clinical examination during the screening period.

- 3.26 Major surgery ≤ 14 days prior to registration.
- 3.27 Systemic treatment with strong CYP3A inducers (rifampin, rifapentine, rifabutin, carbamazepine, phenytoin, phenobarbital) or use of Ginkgo biloba or St. John's wort ≤ 14 days prior to registration.
- 3.28 Uncontrolled intercurrent illness including, but not limited to, ongoing or active infection, symptomatic congestive heart failure, unstable angina pectoris, cardiac arrhythmia, or psychiatric illness/social situations that would limit compliance with study requirements. **NOTE:** Any ECG abnormality at screening must be documented by the investigator as not medically relevant.
- 3.29a QTc > 470 milliseconds (msec) on a 12-lead ECG obtained during the Screening period.

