- 2) Affected immunoglobulin refers to the baseline M-protein type, that is, IgG, IgA, or IgD. Not applicable if patient “non-secretory” or if patient has no heavy chain, i.e. light chain myeloma. Affected immunoglobulin is required after baseline only if it used for disease monitoring instead of SPEP (e.g. IgA myeloma).
- 3) Urine Electrophoresis required only if used to assess disease response.
- 4) Immunofixation (IF) needed only in the absence of M-protein to document sCR or CR.
- 5) Serial light chain required if it is used for disease monitoring (measurable disease at baseline)
- 6) Every 365 days (12 months) or more often if clinically indicated.
- 7) Does not need to be repeated at Cycle 1 Day 1. Baseline values can be used for cycle 1.
- 8) This test is not mandatory. CT or MRI or the CT portion of the PET/CT, same modality should be used at baseline and for serial evaluation. PET/CT scans are required at baseline for all patients with suspected extra-medullary disease (EMD). Assessment of EMD lesions should be performed at end of induction, post ASCT (range:day 60-120), post consolidation (if persistent EMD noted previously) and every year on maintenance or more frequently if clinically indicated. For patients with only skin involvement, skin lesions should be measured with a ruler with images maintained in the medical record.
- 9) Number of circulating cells may be measured using flow cytometry or peripheral smear as is the standard practice for the institution, but same methodology should be used at every time point. This should be repeated after Cycle 1 and every 2 cycles after that or more often if clinically indicated.
- 10) At the end of 4 cycles and only required to document CR after that and assess MRD. If a bone marrow was done to confirm CR prior to end of 4 cycles, no further bone marrow examination until the end of the phase (induction/~ day 100 post –ASCT, consolidation and annually while on maintenance if CR suspected).
- 11) For persons of childbearing potential only. Must be done ≤ 7 days prior to registration.

- 12) All study participants must be registered into the mandatory POMALYST REMS™ program, and be willing and able to comply with the requirements of the POMALYST REMS™ program.

FOOTNOTES CONTINUE ON NEXT PAGE

- 13) The diary must begin the day the patient starts taking the medication and must be completed per protocol and returned to the treating institution.

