11.6 Criteria for engraftment (for hematopoietic stem cell transplant studies only)

Engraftment is defined as:

- The first day of three consecutive days on which the absolute neutrophil count (ANC) $>500/\text{mm}^3$

and

- The first of three consecutive days with an untransfused platelet count $>20,000/\text{mm}^3$.

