16.33 Correlative Analyses

- 16.331 Minimal residual disease will be assessed on bone marrow aspirate in all patients in CR at various stages of treatment: after induction, day # 100 after SCT, after consolidation and during maintenance at one year from initiation of maintenance therapy. The proportion of patients who achieve MRD negative status will be estimated by the number of patients who are MRD negative divided by the total number of evaluable patients who achieve an sCR or CR. Exact binomial 95% confidence intervals for the true MRD negative rate will be calculated.

- 16.324 Engraftment kinetics (WBC and platelet) following single salvage ASCT for relapsed disease will be measured by assessing the timing of recovery of bone marrow function. Neutrophil engraftment will be defined as the first of the three days of neutrophil count above 500/microliter and platelet engraftment as the first day of >20,000 platelets/microliter, untransfused.. The median time to engraftment of neutrophil count and platelet count from the day of infusion of autologous stem cells (day 0) will be summarized using descriptive statistics.

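### The 3-day platelet-transfusion ban runs from registration and dosing days, not from the qualifying blood draw, so a count raised by a recent transfusion can meet the 3.13 platelet floor (minor)

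*Combined protocol and SAP*

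**What the plan says.** **Eligibility floor.** Section 3.13 introduces the laboratory criteria with "The following laboratory values obtained" and allows draws up to 14 days before registration. The platelet floor is 75 x 10^9/L. It is relaxed for patients with at least 50% "bone marrow infiltration in which case a platelet count of" 50 x 10^9/L or more. Nothing in 3.13 mentions transfusion.

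**Transfusion notes.** A note under 3.21, the prior-malignancy exclusion, says: "Platelet transfusions to help patients meet eligibility criteria are not allowed" in the 3 days before registration. Section 9.5 repeats the note and adds dosing days; there, such transfusions are "not allowed within 3 days prior to study registration or drug dosing for any dosing day". The general rule at the start of 9.5 is: "Blood products and growth factors should be utilized as clinically warranted and following institutional policies and recommendations".

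**First dose.** Section 6.6 lets treatment start up to 14 days after registration. Footnote 7 of the 4.1 test schedule says of the pre-cycle tests: "Does not need to be repeated at Cycle 1 Day 1. Baseline values can be used for cycle 1".

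**The concern.** The notes state their own purpose: transfusions should not be what makes a patient eligible. Eligibility on platelets is decided by one measurement, the count under 3.13, yet the exclusion interval is tied to other dates. If the draw comes several days before registration, the interval does not reach back to the transfusion that could have lifted the count.

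At stake is the entry safeguard. A patient whose unsupported count is below the floor could be registered as eligible and start ixazomib with pomalidomide. Sections 15.17 and 15.27 list thrombocytopenia as very common with both drugs, and Table 1-3 gives 28% in the pooled oral ixazomib combination studies. Section 9.9h also calls for daily aspirin 325 mg, or therapeutic anticoagulation if thrombotic risk is high.

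**Working it through.** The plan gives no figure on this point, so the check is a calendar one.

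**Inputs.** Registration is day 0. The draw day d runs from -14 to 0 (3.13). Eligibility transfusions are barred on days -3 to 0 (3.21 note and 9.5). The first dose falls on a day f from 0 to 14 (6.6), and 9.5 also bars days f - 3 to f.

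**Step 1: what the registration ban leaves open.** A transfusion on day t before registration is permitted if t is -4 or earlier. For a draw on day d, the latest permitted transfusion day is the earlier of d and -4, so the smallest permitted gap is d - min(d, -4).

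| Draw day d | Latest permitted transfusion | Smallest gap (days) |
|---|---|---|
| -14 to -4 | same day as the draw | 0 |
| -3 | -4 | 1 |
| -2 | -4 | 2 |
| -1 | -4 | 3 |
| 0 | -4 | 4 |

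A gap of 0 proves little, because a same-day transfusion may follow the draw. A transfusion on the day before the draw certainly precedes it, and it is permitted when d - 1 is at most -4, that is for any draw from day -14 to day -3.

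**Step 2: worked example.** With t = -6, d = -5 and registration on day 0, the transfusion precedes the draw by 1 day and registration by 6. It lies outside days -3 to 0, and the draw lies inside days -14 to 0. Both notes and the 3.13 window are satisfied.

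**Step 3: does the dosing-day ban catch it?** The earliest barred day is f - 3. With f at least 0, that is day -3 or later. A transfusion on day -4 or earlier is never caught, whatever the first dosing day.

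**Step 4: is a fresh count required before the first dose?** No. Section 8.11 sets the same platelet floor for starting a new cycle, but footnote 7 lets baseline values stand for Cycle 1. The count can be 14 + 14 = 28 days old at first dose.

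**Step 5: effect of the fix.** If a count drawn within 3 days after a transfusion cannot be used, the smallest gap behind any usable count is 4 days on every draw day. In the example, the day -5 count is set aside and a repeat from day -2 onward (-6 + 4) is usable.

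**Side check on the design.** With 21 evaluable patients and success at 14 or more, the binomial tail is 0.0946 at a true proportion of 0.50 and 0.8701 at 0.75. These match the stated 0.095 and 0.870 in 16.24, and the transfusion rule enters neither.

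**The case against.** The strongest reply is that little harm can follow. The test schedule (footnote 16) requires blood counts on Days 8, 15 and 22 of Cycles 1 to 3. Tables 8.2 and 8.3 omit ixazomib and pomalidomide when platelets fall below 30 x 10^9/L. Section 8.11 re-applies the floor at later cycles. Transplant eligibility (3.12) and investigator judgement (3.23) are further screens. This stands as a limit on consequence: a misleading entry count would normally show about a week after the first dose. It does not repair the entry rule. The in-cycle threshold of 30 is below the entry floor of 75 or 50, so a patient between the two would not meet the floor unsupported but would not trigger omission either.

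A second reply is that tying the ban to registration and dosing days was the sponsor's choice. That is possible, but the notes name eligibility as their purpose, and the chosen dates miss the measurement that decides it.

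Three stronger readings are tempting, and the documents do not support them:

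- *The ban is useless.* It bars eligibility transfusions on days -3 to 0, and a draw on day 0 has a full 4-day gap.
- *The sponsor meant eligibility counts to be wholly untransfused.* Sections 11.6 ("The first of three consecutive days with an untransfused platelet count") and 16.324 ("platelet engraftment as the first day of >20,000 platelets/microliter, untransfused") do use that condition, but they define marrow recovery after transplant, where it is part of the outcome. They show that the plan can state the condition, not that 3.13 intended it.
- *The share of calendar days left open measures the problem.* Draw days are not equally likely and days are not patients, so no rate follows.

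**Conclusion.** The gap is real, and nothing else in the protocol closes it: a count drawn shortly after a platelet transfusion can meet the 3.13 floor without breaching either note. It is a minor eligibility and safety point. The decision rule, alpha, power and the definition of the 18-month progression-free endpoint do not change. The documents give no data on platelet transfusion at screening, so the number affected cannot be derived; with 25 patients planned, it is probably small.

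Two assumptions apply. The 3-day interval is taken from the sponsor; the documents do not show that 3 days is long enough for a count to become unsupported. The calendar check reads both notes literally, with day -3 barred and day -4 allowed.

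A reader might infer that correcting the wording would assure a safe count at first dose. It would not, because the qualifying count may still be up to 28 days old by then.

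**What to change.** Keep the existing registration and dosing-day bans. Add to 3.13, beside the platelet criterion:

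*A platelet count drawn within 3 days after a platelet transfusion may not be used to meet this criterion; repeat the count before registration.*

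Add a cross-reference to it in the 3.21 and 9.5 notes. The sentence disqualifies the count; it does not forbid the transfusion. That matters because a ban on transfusion before the draw would conflict with the opening rule of 9.5 on clinically warranted use. It also works whatever the reason for the transfusion. No further limit is needed between draw and registration, since a transfusion given after the draw cannot have raised that count.

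The cost is one sentence, two cross-references and an occasional repeat blood count, with a possible delay of a few days to registration for a patient transfused shortly before the screening draw.
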